7.3 Major Hypotheses

(All hypotheses are presented “under the alternative”)

Primary Hypothesis:

On average, participants will have a higher absolute increase in levels of cell-associated HIV RNA transcription in CD4⁺ T-cells seven days after receiving either Pneumococcal or Influenza vaccinations, when compared to seven days after receiving placebo.

Secondary Hypotheses:

- Among the five participants with the largest increases in cell-associated HIV RNA in CD4⁺ T-cells following active vaccination (maximum across all observed time-points), we will deep sequence cell-associated HIV RNA and DNA populations at 0, 2, 4, 7, 14 and 30 days. We hypothesize that active vaccines will *non-selectively* activate cellular transcription of HIV, as evaluated by panmixis tests between sequences of HIV DNA and RNA populations at these sampled timepoints.
- On average, participants will have a greater absolute maximum decrease in levels of total CD4⁺ T-cell-associated HIV DNA measured 2-30 days after receiving either Pneumococcal or Influenza vaccinations, when compared to 2-30 days after receiving placebo.
- Among the five participants with the largest increases in cell-associated HIV RNA in CD4⁺ T-cells following active vaccination (maximum across all observed time-points), we will perform inducible RNA assay. We hypothesize that these five participants will have lower levels of replication competent proviruses 30 days after active vaccination, as compared to their levels of replication competent proviruses sampled before this vaccination.
- Participants will have a greater absolute maximum increase in levels of (a) inflammatory cytokines, (b) T-cell activation and proliferation, (c) HIV-specific immune responses, and (d) vaccine-specific immune responses over the 30 days of observation after receiving either active vaccination, when compared to maximum measures taken over the 30 days of observation after receiving placebo.

- Levels of non-antigen specific immune stimulation (cytokines and general T-cell activation) and vaccine-specific immune responses will be positively associated with increased CD4⁺ T-cell-associated HIV RNA transcription and negatively associated with lower levels of HIV DNA, over the 30 days of observation after receiving either Pneumococcal or Influenza vaccinations.

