- Maximum levels of cell-associated HIV RNA over the 30 days of observation following active vaccination will be positively associated with HIV-specific responses 30 days after receiving active vaccinations.
- Genital shedding of human herpesviruses, increased levels of microbial translocation and incident illnesses will stimulate the immune system and induce increased cell-associated HIV RNA transcription from CD4⁺ T-cells in participants independent of receiving active vaccine or placebo.
- Presence of dysbiosis (for example increased relative frequency of Proteobacteria in stool samples) will be associated with increased microbial translocation and with increased cell-associated HIV RNA transcription from CD4⁺ T-cells in participants independent of receiving active vaccine or placebo.

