8.2.5 Aim 3b

Determine if immune stimulation associated with active vaccination is associated with reduction in number of HIV DNA populations.

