9.5. Sample collection

Study evaluations will be based on three 30 day cycles (Influenza vaccine, Pneumococcus vaccine, Placebo in random order) over 28 weeks of the RCT. *Pre injection*: one paired blood, optional stool and optional genital secretion sample will be collected before each injection. *Post-injection*: Blood samples will be collected on days 2, 4, 7, 14 and 30 after each injection. Optional genital secretion samples will be collected on days 14 and 30 after each injection; see **Table 1 Schedule of Evaluations**.

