12.2 Laboratory Evaluations

All laboratory procedures will be conducted in accordance with Good Clinical Laboratory Practices (GCLP) according to the [DAIDS guidelines](#).

A urine pregnancy test will be performed at screening in women who can become pregnant and will be repeated only if pregnancy is suspected.

A rapid HIV test will be performed if no documentation of previous HIV infection is provided.

Table 3 is a summary table of study assays, methods and time points.

	Measurements	Methods	Sample	Sampled Time-points (Days)
Virologic (Aims 1+2)	Cell-associated HIV RNA levels	(dd)PCR	PBMC (CD4+)	
	HIV DNA levels (pol and 2-LTR)	(dd)PCR	PBMC (CD4+)	0, 2, 4, 7, 14, 30 after each injection
	Cell-free HIV RNA levels	SCA	Blood plasma	
	Cell-associated HIV RNA diversity*	env NGS	PBMC (CD4+)	0 and time point with highest cell associated HIV RNA level after the active vaccination
	Cell-associated HIV DNA diversity*	env NGS	PBMC (CD4+)	
	Replication competent HIV levels*	DNA Inducible RNA assay	PBMC (CD4+)	0 and 30 after each active vaccine
Immunologic	Soluble inflammation markers	ELISA	Blood plasma	0, 2, 4, 7, 14, 30 after each injection

(Aim 3)	Vaccine-specific response	ELISA	Blood plasma	
	Cellular inflammation markers	Flow	PBMC	
	HIV-specific T-cell response	Flow ICC	PBMC	
Incidental stimulation	Microbiome Composition	r16s Sequencing	Stool	Day 0
	HHV quantification	qRT-PCR	GS	0, 14, 30 after each injection
	Incident Illness surveys	Survey	--	

Legend: ddPCR: digital droplet PCR, SCA: single copy assay, PBMC: peripheral blood mononuclear cells, ELISA: enzyme linked immunoassay, Flow: flow cytometry, ICC: intracellular cytokine staining, qRT-PCR: quantitative real time PCR. GS: genital secretion. *The 5 participants with the highest sum levels of cell-associated HIV RNA within the 30 days (five measures) following both active vaccinations will undergo these assessments. These same 5 participants will be used for both of these analyses.

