15.2 Study Endpoints

15.2.1 Primary Endpoint

Average change in level of CD4+ T-cell-associated HIV RNA transcription from baseline to 7 days after each injection.

15.2.2 Secondary Endpoints:

1. Average change in level of CD4+ T-cell-associated HIV RNA transcription from baseline to 2, 4, 14 and 30 days after each injection.
2. Average change in levels of HIV DNA from baseline to 2, 4, 7, 14 and 30 days after each injection.
3. Determine selective vs. nonselective HIV RNA production from HIV DNA (by next generation sequencing and panmixis tests) among the five participants with the highest levels of cell associated HIV RNA following active vaccination.
4. Average change in levels of immune activation (soluble and cellular markers) from baseline to 2, 4, 7, 14 and 30 days after each injection.
5. Average change in levels of replication competent HIV DNA (by inducible RNA assay) among the five participants with the highest levels of cell associated HIV RNA following active vaccination.
6. Average change in levels of HIV specific T-cell immune response from baseline to 30 days after each injection.
7. Stimulation of HIV transcription by incidental illness, human herpesviruses replication and microbial translocation over the course of the study.
8. Possible immunomodulatory effect of microbiome composition
9. Vaccine administration will be safe for all included participants.

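### The secondary hypothesis linking maximum HIV RNA level to the Day 30 HIV-specific response ignores both Day 0 values, so it cannot separate vaccine-induced change from standing differences between participants

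*Combined protocol and SAP*

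**What the plan says.** Section 7.3 sets the association out in these terms: "Maximum levels of cell-associated HIV RNA over the 30 days of observation following active vaccination will be positively associated with HIV-specific responses 30 days" after active vaccination. It names no Day 0 value, adjustment or placebo comparison.

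The window holds five post-injection samples. Section 9.5 says: "Blood samples will be collected on days 2, 4, 7, 14 and 30 after each injection". The legend to Table 3 in 12.2 counts the same five when it ranks participants on RNA "within the 30 days (five measures) following both active vaccinations". Day 30 is therefore one of the values that can be the maximum, and it is also the day on which the response is read.

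The endpoint list handles the same two quantities differently. The primary endpoint in 15.2.1 is "Average change in level of CD4+ T-cell-associated HIV RNA transcription from baseline to 7 days after each injection", and 15.2.2 item 1 extends that change to the other sampling days. Item 6 of 15.2.2 is "Average change in levels of HIV specific T-cell immune response from baseline to 30 days after each injection".

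The preceding hypothesis in 7.3 says immune stimulation will be "negatively associated with lower levels of HIV DNA, over the 30 days of observation" after active vaccination. Aim 3b (8.2.5) reads: "Determine if immune stimulation associated with active vaccination is associated with reduction in number of HIV DNA populations". Another hypothesis in 7.3 expects a larger maximum fall in total HIV DNA after active vaccine than after placebo.

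Section 15.8.2 gives no model for either association. It refers additional analyses to a Statistical Analysis Plan whose text is not in the supplied document.

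**The concern.** A participant's maximum RNA after vaccination is the standing level plus any induced rise plus assay and day-to-day noise. The Day 30 response likewise carries whatever HIV-specific immunity was there before the injection. If participants with more RNA at rest also tend to have stronger HIV-specific responses at rest, the two raw quantities will correlate even if the vaccine does nothing. Randomising the order of injections gives no protection, because the association is examined across participants within the active cycles.

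The documents make standing differences plausible. Section 7.1.4 reports that participants with CMV replication had more T-cell activation, higher proviral DNA and higher cellular RNA, without vaccination being involved. Section 15.4 gives HIV DNA a mean of 41.01 and an SD of 75.01 in 199 subjects. Neither supplies the correlation that matters here, between resting RNA and HIV-specific response.

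There are two smaller issues. Because the maximum may be the Day 30 sample, the wording does not secure that the RNA rise comes before the response. And the DNA sentence, taken literally, predicts the opposite of the reduction that Aim 3b looks for.

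**Working it through.** **1. The plan's own figure.** The documents give no figure for this association. The nearest is the detectable difference in 15.4: n = 50, SD 625, two-sided alpha 0.05, 80% power, stated as 253 copies/10^6 CD4 T-cells. The normal approximation is 625 × (1.960 + 0.842) / √50 = 247.6. The paired t-test (noncentral t, 49 df) gives 252.6, with power 80.1% at 253. The figure reproduces and is not in dispute.

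**2. Set-up.** There were 4,000 simulated trials of 50 participants per setting.
- From the plan: n = 50; SD of RNA change 625; sampling days 2, 4, 7, 14, 30; two-sided 0.05 (the level 15.8.2 sets for the primary tests).
- Assumed: person-level SD of induced rise 550 and per-sample noise SD 210, chosen so that √(550² + 2 × 210²) = 625; mean induced rise 250; relative size by day 0.4, 0.7, 1, 0.7, 0.4 (peak at Day 7); SD of standing RNA 300 to 2,000; correlation ρ between standing RNA and HIV-specific response 0 to 0.5.
- Model: RNA on day d = standing level + induced rise × relative size(d) + noise. Day 0 RNA = standing level + noise. The Day 30 response depends on standing level through ρ and, where stated, on induction through a true correlation of 0.4.
- Test: Pearson correlation of the response with (a) the raw maximum over days 2–30, (b) that maximum minus Day 0 RNA, (c) the raw maximum adjusted for Day 0 RNA. The window is the same in all three, and the response is left as its Day 30 value.

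**3. No induction–response link: share of trials significant with the raw maximum.**

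| SD of standing RNA | ρ = 0 | ρ = 0.2 | ρ = 0.3 | ρ = 0.5 |
|---|---|---|---|---|
| 300 | 5.1% | 12.3% | 23.5% | 54.4% |
| 625 | 5.5% | 21.3% | 42.4% | 85.9% |
| 1,250 | 5.4% | 27.0% | 53.4% | 94.8% |
| 2,000 | 4.7% | 27.8% | 54.5% | 96.2% |

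With (b) the rate is 4.5–5.4% in every cell. With (c) it is about 5–8% in most cells and reaches 13.8% at SD 300 and ρ = 0.5, because a noisy Day 0 value adjusts incompletely.

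**4. True induction–response correlation 0.4, ρ = 0.** The raw maximum is significant in 59.1%, 31.4%, 13.7% and 8.0% of trials at standing SD 300, 625, 1,250 and 2,000. Change from Day 0 gives 66–67% throughout. The raw maximum therefore does carry induction signal, diluted by standing variation.

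**5. Second simulation, log10 scale.** With assumed person SD 0.5 and noise 0.25, the level-based test is significant in 21%, 42% and 67% of trials at baseline correlation 0.2, 0.3 and 0.4, against about 5% for changes. Its change version also shortened the RNA window to days 2–14, so step 3 is the cleaner comparison.

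**6. DNA direction.** A negative association with lower DNA means that more stimulation goes with higher DNA. Aim 3b and the DNA-decrease hypothesis both point to less DNA. The sentence contains one negation too many.

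**The case against.** A hypothesis sentence is not an analysis specification. It names no test or covariates, 15.8.2 defers further analyses to a SAP, and 15.2.2 already defines both quantities as changes. The documents also use *levels* loosely: the five participants selected for sequencing are those with the largest increases in 7.3 and those with the highest levels in 15.2.2. Day 0 adjustment may well be intended. That is a fair reading, but it does not settle the matter. The hypothesis as written and the endpoints as defined call for different analyses, and nothing supplied says which one governs.

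The false-positive rates also rest on assumed inputs. No baseline RNA SD is given, nor any correlation of RNA with HIV-specific response, and at zero correlation the raw test is sound. This stands: the rates show sensitivity and do not estimate what this trial would produce.

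Three stronger inferences are tempting, and the documents do not support them:
- *The hypothesis measures reservoir size and not induction.* Step 4 shows that a raw maximum responds to both, and the share due to each cannot be fixed from the documents.
- *A positive result is to be expected from between-person differences alone.* Even at the assumed correlations of 0.2 and 0.3, 72–88% and 45–76% of null trials are not significant.
- *Day 30 must be dropped from the RNA maximum.* Section 7.2 reports the pilot RNA signal 30 days after vaccination, so removing that day discards the time point behind the trial's own evidence.

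Whether vaccination raises HIV-specific immunity is tested elsewhere in 7.3, by comparing maximum increases after active vaccine and after placebo. That comparison is not exposed to this problem.

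**Conclusion.** The point holds in limited form. As written, the hypothesis cannot separate vaccine-induced change from standing between-person differences, and it departs from the change-from-baseline endpoints in 15.2.2 items 1 and 6.

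If standing RNA and HIV-specific response are correlated, the level-based test rejects too often: 12–28% at 0.2 and 24–55% at 0.3, over an assumed standing RNA SD of 300 to 2,000. At zero correlation, or with RNA as change from Day 0, it is about 5%. That last figure assumes the induced rise does not depend on standing level. Section 9.4 expects a large reservoir to make an effect easier to see, so change scores may not remove all of the dependence. This is a reason to report the placebo cycle as well.

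The reversed DNA phrase is a drafting slip. A reader might infer that the trial is set up to test the wrong direction, but Aim 3b and the DNA-decrease hypothesis make the intended direction clear.

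Both matters concern secondary hypotheses only.

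**What to change.** - Restate the hypothesis in 7.3 along these lines: *the maximum increase from the same cycle's Day 0 in cell-associated HIV RNA over days 2–30 after active vaccination will be positively associated with the increase in HIV-specific response from Day 0 to Day 30 of that cycle.* Adjusting for both Day 0 values is an acceptable alternative, with the residual confounding noted in step 3.
- Report the same association in the placebo cycle as the reference.
- Keep days 2–30 as the main RNA window. Add RNA limited to days 2–14 as a sensitivity analysis for temporal order.
- In the preceding hypothesis, delete one word so that stimulation is *negatively associated with levels of HIV DNA*. Aim 3b concerns the number of HIV DNA populations, a different quantity, and need not be rewritten.
- Settle this before the unblinding described in 15.8.2, so that the choice between levels and changes is not made after seeing results.

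The cost is wording and one re-specified secondary analysis. Section 12.3.4.2 already has RNA and HIV-specific T-cell response measured at each injection and at the five later visits, so no visit or sample is added. Change scores can be noisier than levels, and a true association may look weaker where standing variation is small relative to assay noise. The days 2–14 analysis would miss late peaks, which is why it should not be the main one.

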8. OBJECTIVES

8.1 Primary Objective

Determine the impact of Pneumococcus and Influenza vaccines on the HIV transcriptional activity in individuals who are virologically suppressed for at least 48 weeks on ART.

8.2 Secondary Objectives

8.2.1 Aim 1a

Determine the timing and duration of increased HIV transcription following active vaccination.

8.2.2 Aim 1b

Determine if vaccination selectively or non-selectively activates HIV transcription from HIV DNA populations

8.2.3 Aim 2

Determine if active vaccination influences levels of cell associated HIV DNA or replication competent provirus.

8.2.4 Aim 3a

Determine to what degree immune stimulation with an Influenza or Pneumococcal vaccine can induce HIV transcription during ART.

8.2.5 Aim 3b

Determine if immune stimulation associated with active vaccination is associated with reduction in number of HIV DNA populations.

8.2.6 Aim 3c

Determine if HIV-specific, vaccine-specific, or bystander immune stimulation is associated with HIV transcription.

8.2.7 Aim 4

Determine how genital shedding of human herpesviruses, microbial translocation and incident illnesses stimulate the immune system and influence levels HIV transcription.

8.2.8 Aim 5

Determine how dysbiosis contribute to stimulate the immune system and influence HIV transcription.

9. STUDY DESIGN

The proposed study is a randomized double-blinded control trial conducted over 28 weeks. Randomized interventions will be injections of Influenza vaccine, Pneumococcal vaccine, and Placebo. Each participant will receive each injection but in a randomized order.

9.1. Vaccines

Influenza (Fluarix®, GSK or Fluzone®, Sanofi -Pasteur), Pneumococcal (Pneumovax®23, Merck), and placebo (sterile saline injection).

NOTE: Fluarix® quadravalent vaccine is the flu vaccine of choice for this study. Fluzone® quadravalent vaccine may be substituted for Fluarix® only in the event that Fluarix® is unobtainable from the wholesaler/manufacturer.

9.2. Primary endpoint

average change in level of CD4+ T-cell-associated HIV RNA transcription from baseline to day 7 after each injection.

9.3. Study Arms

Each subject will take Influenza (Fluarix®, GSK or Fluzone®, Sanofi -Pasteur), Pneumococcal (Pneumovax®23, Merck), and placebo. Randomization will determine the order in which the subjects receive the injections. There are six possible study arms, one for each order in which someone can receive the injections:

Placebo, Flu, Pneumovax

Placebo, Pneumovax, Flu

Flu, Placebo, Pneumovax

Flu, Pneumovax, Placebo

Pneumovax, Placebo, Flu

Pneumovax, Flu, Placebo

9.4. Study population

This study will enroll 56 HIV-infected individuals between the ages of 18 and 65 who started ART during chronic infection. These subjects will be recruited from both the UCSD AntiViral Research Center and the Owen Clinic. Eligible participants will have CD4 >250 cells/ μ l at enrollment and a CD4 nadir >100 cells/ μ l. We chose to limit enrollment to younger individuals with higher CD4 counts to enhance the likelihood of having a more robust immune response to any given vaccine. We limited enrollment to individuals who started ART during chronic infection (at least one-year from estimated date of infection) to enhance the likelihood of having a large replication competent viral reservoir, thus increasing our chances to observe an effect of vaccine administration on HIV RNA transcription [96]. To reduce variability in vaccine stimulation (between antigen naïve versus experienced participants), we will also limit participation to individuals who have documented or reported vaccine history consistent with previous influenza and pneumococcal vaccination.

9.5. Sample collection

Study evaluations will be based on three 30 day cycles (Influenza vaccine, Pneumococcus vaccine, Placebo in random order) over 28 weeks of the RCT. *Pre injection*: one paired blood, optional stool and optional genital secretion sample will be collected before each injection. *Post-injection*: Blood samples will be collected on days 2, 4, 7, 14 and 30 after each injection. Optional genital secretion samples will be collected on days 14 and 30 after each injection; see **Table 1 Schedule of Evaluations**.

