Optional Stool Collection		X						X						X						
Optional Genital Secretion ^d		X				X	X	X				X	X	X				X	X	X
Hematology/Chemistry/Coagulation Panel		X				X	X	X				X	X	X				X	X	X
Immune responses		X	X	X	X	X	X	X	X	X	X	X	X	X	X	X	X	X	X	X
HIV-1 RNA sequencing		X	X	X	X	X	X	X	X	X	X	X	X	X	X	X	X	X	X	X
CD4+ T-cell Count		X	X	X	X	X	X	X	X	X	X	X	X	X	X	X	X	X	X	X
HIV-1 DNA sequencing		X	X	X	X	X	X	X	X	X	X	X	X	X	X	X	X	X	X	X
Archive Plasma		X	X	X	X	X	X	X	X	X	X	X	X	X	X	X	X	X	X	X

- Cycle 1 to begin within 30 days of screening visit
- ± 2 days
- Minimum 6 week washout period between cycles
- Paired blood and optional genital secretion sample will be collected **before** each injection
- Pregnancy Test will be repeated only if pregnancy is suspected.

Study Duration: 240 weeks

[figure not shown]
Study Regimen/Intervention: This is a double blind RCT of two vaccines (Pneumovax®23 and Fluarix® or Fluzone®) plus placebo (sterile saline injection). Study participants will be followed for 28 weeks after enrollment. During this 28-week period, blood samples will be collected on day 0 and five subsequent time points after each injection (days 2, 4, 7, 14 and 30). Optional genital secretion samples will be collected on day zero and on days 14 and 30 after each injection. Optional stool will be collected at day zero. Injections (vaccine or placebo) will be administered 12 weeks apart and in a random order, to minimize a possible bias due to the order of the vaccines.

NOTE: Fluarix® quadravalent vaccine is the flu vaccine of choice for this study. Fluzone® quadravalent vaccine may be substituted for Fluarix® only in the event that Fluarix® is unobtainable from the wholesaler/manufacturer.

Primary Objective: To determine the impact of Pneumococcus and Influenza vaccines on the HIV transcriptional activity in individuals who are virologically suppressed for at least 48 weeks on ART.

Primary Outcome: Average change in level of CD4+ T-cell-associated HIV RNA transcription from baseline to day 7 after each injection.

Figure 1. Study Design and sampling

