15.8.2 Analysis Plan

All formal analyses of the data will be performed at the end of the study with no real time clinical decisions based on intermediate results. We will utilize a comprehensive AVRC Data Management System developed through our CFAR that can handle all dynamic aspects of clinical research studies including electronic case report form (eCRF) creation and editing, protocol design interfaces, online data entry and QA workflows, real-time accrual monitoring, multi-study data integration, role-based user permissions, integrated specimen processing workflows, an auditing system to track changes to both forms and data, and data visualization and export tools.

Sample and data collection from study participants will occur from study months 6-36 of the study. Unblinding of the study arms for data analysis of primary and secondary endpoints will occur around 44-48 months (after all participants have completed the entire study follow-up), and the final analysis of the trial will take place between 48 and 60 months.

Analysis of the Primary Hypothesis: We will determine whether average changes in levels of cell-associated HIV RNA in CD4+ T-cells are associated with administration of active vaccine or placebo using two-sided paired t-tests with alpha level of 0.05 for each of the two tests (influenza versus placebo and pneumococcus versus placebo).

Secondary analyses: Since subjects will receive multiple injections, we will determine if changes in cell associated HIV RNA in CD4+ T-cell levels are sustained over the weeks following vaccination using graphical and descriptive statistical methods. We will also explore the effect of the vaccines on the size of cell free and cell associated HIV RNA populations using linear mixed effects models and consider incorporating interactions with time to evaluate the change in effects of the vaccines over time.

Additional analyses are described in the Statistical Analysis Plan (SAP).

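### The common ±2-day window makes adjacent early visits overlap (Day 2 with Day 4, Day 4 with Day 7), so results by nominal day blur the timing of the HIV RNA response within the first week.

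*Combined protocol and SAP*

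**What the plan says.** Section 9.5 sets the post-injection schedule: "Blood samples will be collected on days 2, 4, 7, 14 and 30 after each injection". In Table 1 (section 6) every Day 2, 4, 7, 14 and 30 column, in all three cycles, carries marker b. The footnotes below the table follow in order: the first is "Cycle 1 to begin within 30 days of screening visit", the second is ±2 days and the third is the washout. Marker a sits on Cycle 1 and marker c on Cycles 2 and 3, so this order fits and footnote b is the ±2-day window.

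Aim 1a (8.2.1) is to "Determine the timing and duration of increased HIV transcription following active vaccination". Secondary endpoint 1 (15.2.2) is "Average change in level of CD4+ T-cell-associated HIV RNA transcription from baseline to 2, 4, 14 and 30 days after each injection", and the primary endpoint (15.2.1) is "Average change in level of CD4+ T-cell-associated HIV RNA transcription from baseline to 7 days after each injection". Both are defined by nominal day.

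For analysis, 15.8.2 will look at whether changes "are sustained over the weeks following vaccination using graphical and descriptive statistical methods". It also plans linear mixed effects models and will "consider incorporating interactions with time to evaluate the change in effects of the vaccines over time". It does not say whether time means the scheduled visit or the actual day since injection. It adds: "Additional analyses are described in the Statistical Analysis Plan (SAP"; no text of that plan is in the material supplied. Nothing supplied sets a minimum gap between visits or a rule for assigning a sample to a visit.

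**The concern.** A tolerance of ±2 days is modest at Day 30 but equals the whole elapsed time at Day 2. Early sampling is where the schedule is densest and where the response could change fastest. If results are summarised by visit label, the Day 2 and Day 4 means can draw on the same actual days, and some Day 2 samples may carry no post-injection time at all. An early rise would then look lower and flatter than it was.

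This bears on the study's own case. Section 7.1.2 attributes the inconsistent earlier findings partly to varying sampling times and offers better-chosen times as an improvement. What is at stake is the timing half of Aim 1a and secondary endpoint 1. Sampling days cannot be tightened after the blood has been drawn.

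**Working it through.** **The plan's own figure.** The plan gives no figure for timing. The stated figure for the HIV RNA endpoint, a detectable difference of 253 copies/10⁶ CD4 T-cells in 15.4 (N = 50, SD 625, 80% power, two-sided 0.05), reproduces as 252.6 with a paired t-test. This point does not depend on it.

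**Windows** (nominal day ±2, whole days; inputs from 9.5 and Table 1 footnote b)

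| Visit | Allowed days | Shared with next visit |
|---|---|---|
| Day 2 | 0-4 | 2, 3, 4 |
| Day 4 | 2-6 | 5, 6 |
| Day 7 | 5-9 | none |
| Day 14 | 12-16 | none |
| Day 30 | 28-32 | - |

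Day 2 and Day 7 share no day. The Day 2 window reaches Day 0.

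**How often labels and days could disagree.** Assume each allowed day is equally likely and visits are independent. Then 1/5 = 20% of Day 2 draws fall on Day 0. The Day 4 draw falls on or before the Day 2 draw in 6 of 25 combinations (24%; 3 coincide and 3 reverse). The Day 7 draw falls on or before the Day 4 draw in 3 of 25 (12%). With weights 1:2:3:2:1 around the target, 1/9 = 11% of Day 2 draws fall on Day 0. Comparing draws from different participants under these weights, the two shares are about 18% and 6%. The documents give no attendance pattern, so these are assumptions.

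**Effect on the visit means.** Assume a response that starts at zero and peaks at Day 2: f(t) = (t/2)·exp(1 − t/2). Its values on days 0 to 6 are 0, 0.824, 1, 0.910, 0.736, 0.558, 0.406.

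- Exact sampling: Day 2 = 1.00, Day 4 = 0.74, contrast 0.26.
- ±2 days, even: Day 2 = (0 + 0.824 + 1 + 0.910 + 0.736)/5 = 0.69; Day 4 = (1 + 0.910 + 0.736 + 0.558 + 0.406)/5 = 0.72. Day 2 is understated by 31% and Day 4 is marginally higher.
- ±2 days, weights 1:2:3:2:1: Day 2 = (0 + 2×0.824 + 3×1 + 2×0.910 + 0.736)/9 = 0.80; Day 4 = (1 + 2×0.910 + 3×0.736 + 2×0.558 + 0.406)/9 = 0.73. Understated by 20%; contrast 0.07.
- ±1 day, even: Day 2 = (0.824 + 1 + 0.910)/3 = 0.91; Day 4 = (0.910 + 0.736 + 0.558)/3 = 0.73. Understated by 9%; contrast 0.18.
- ±2 days, even, Day 0 excluded: Day 2 = (0.824 + 1 + 0.910 + 0.736)/4 = 0.87 against 0.72 at Day 4.
- ±2 days, all ordered, distinct, non-Day-0 combinations equally likely: Days 2/4/7 = 0.88/0.67/0.28.

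**Other peaks.** The same curve with its peak at Day 1.5, 2, 3, 4 or 7, under the two ±2-day attendance patterns, gives 10 cases. The visit with the highest mean changes in one: the Day 2 peak with even attendance, 0.69 against 0.72. For a Day 4 peak with even attendance, Days 2/4/7 go from 0.82/1.00/0.83 to 0.66/0.93/0.82. For a Day 7 peak, the Day 7 mean is 0.98.

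**A different shape.** For a symmetric bell peaking at Day 4 (SD 1.5 days) with even attendance, Days 2/4/7 go from 0.41/1.00/0.14 to 0.47/0.68/0.28. The highest visit is unchanged and the contrast shrinks.

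**The case against.** A reader might infer that the overlap leaves Aim 1a unable to show timing at all, or that an early peak will be credited to the wrong visit. The documents do not support either. Day 2 and Day 7 cannot share a day, and Days 14 and 30 stand clear of everything else. Duration is therefore intact, and 15.8.2 judges it on a scale of weeks. The peak moves in only one of the ten cases above, by 0.03, and not once Day 0 draws are excluded. Even attendance is itself unlikely: Table 2 and 18.7 list and pay Baseline and Day 2 as separate visits, so a Day 2 draw on the injection day should be rare. Nor does any section propose a Day 2 peak; 15.4 chose Day 7 as the time point likely to show the largest effect.

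It can also be said that the mixed model in 15.8.2 may use actual days and that the separate SAP may say so. That is possible: the plan leaves the matter open and does not rule it out.

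All of this limits the size of the point. What stands is that the written window permits the overlap and the Day 0 draw, and that nothing supplied says the actual day will be used. Stability of the peak visit under symmetric bells is weaker reassurance than it looks. Such a curve peaking at Day 2 with SD 1.5 or 2.5 days already has 41% or 73% of its peak at Day 0, where change from baseline should be zero. Even where the peak visit is right, the contrast between visits shrinks.

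**Conclusion.** The point holds as a loss of resolution within the first week, affecting the timing part of Aim 1a and secondary endpoint 1. The overlap and the possible Day 0 draw follow directly from Table 1. The size rests on assumed attendance and an assumed response peaking at Day 2: the Day 2 mean is understated by 31% (even), 20% (clustered) or 9% (±1 day, even). Outside the even ±2-day case that allows Day 0 draws, the main effect is a smaller Day 2/Day 4 contrast, not a misplaced peak.

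Duration and the later visits are little affected. So is the Day 7 primary comparison on the gradual curve used here (0.98 of a Day 7 peak). That last statement depends on shape: a bell peaking at Day 7 with SD 2.5, 1.5 or 1 day would average 0.86, 0.68 or 0.50 of its peak under even attendance. The same window applies to vaccine and placebo cycles, so this would dilute a difference and not create one. The point is a worthwhile low-cost improvement, not a threat to the primary test.

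**What to change.** 1. **Main change, 15.8.2.** State that actual days since injection, from the draw date, is the time variable in the linear mixed model and in the plots for Aim 1a and secondary endpoint 1. Report the distribution of actual days at each nominal visit. If the separate SAP already says this, a cross-reference is enough.
2. **Supporting change, Table 1 footnote b, with 9.5 to match.** Require the Day 2, 4 and 7 blood draws on distinct calendar days, in order, none on Day 0, with ±1 day for these three visits. Keep ±2 days for Days 14 and 30.

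The cost is one analysis sentence, one footnote and slightly less booking flexibility for three visits per cycle. With ±1 day the Day 2 and Day 4 windows (1-3 and 3-5) still let different participants share day 3, which is why the first change matters more. An ordered ±1-day schedule exists for an injection on any weekday if the clinic runs Monday to Friday. The documents do not state opening days, and holidays were not considered, so the sponsor should confirm this.
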